4.5.8 Echocardiogram/Multiple-gated Acquisition Scan (ECHO/MUGA)

4.5.8.1 Definitions and Derivations

Left ventricular ejection fraction (LVEF) will be measured by ECHO or MUGA scan at screening, end of treatment (EOT), and as clinically indicated during the study.

4.5.8.2 Presentations

Absolute value, change from baseline and percentage change from baseline will be presented for LVEF.

Box plots of absolute value and change from baseline over time may also be presented

The overall evaluation (normal/abnormal) will be summarized over time.

4.5.9 B-symptoms

4.5.9.1 Definitions and Derivations

B-symptoms are constitutional symptoms defined as any one or more of the following disease-related symptoms or signs:

- Unintentional weight loss of 10% or more within the previous 6 months
- Fevers > 100.5°F or 38.0°C for > 2 weeks without other evidence of infection, or
- Night sweats for > 1 month without evidence of infection.

4.5.9.2 Presentations

B-symptoms results will be listed for all participants and visits.

4.5.10 Other Safety Assessments

4.5.10.1 Definitions and Derivations

Maximum Tolerated Dose (MTD) Evaluation

See Section 9.4.3.1 of the CSP for the definition of a DLT.

After the escalation phase is completed, DLT rates at each dose level will be estimated by isotonic regression (Ji et al, 2010). The weighted least squares regression model conditional on monotonic non-decreasing DLT rates with increasing dose and use the empirical (observed) DLT rates at each dose level as responses and sample sizes at each dose level as weights, along with the pool adjacent violators algorithm (PAVA) to estimate the DLT rate at each dose level using available software (eg, Cytel EAST or the function pava() from the

R package 'ISO'). Given the DLT estimates for each dose level, the MTD will be selected from all tried dose levels that have not been previously declared to be unsafe with a "deescalate to the previous lower dose and the current dose will be never used again due to unacceptable toxicity" (DU) decision according to the mTPI-2 decision table. With this constraint, the MTD is determined as the dose level with the DLT estimate closest to the target toxicity level of "%."

In the case of dose levels with estimated toxicity of equal distance (tied dose levels) from the target toxicity of "%, the following approach is used (Ji et al, 2010) among all tied dose levels the highest dose level with target toxicity "CC" will be selected, unless all tied dose levels have estimated toxicity "CC", in which case the lowest dose level will be selected.

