#### 6.6.1.2 Modified Toxicity Probability Interval

A minimum of and a maximum of participants will be enrolled at a given dose level for Part A. Dose escalation to the next dose level will be conducted using the mTPI-2 algorithm with a target DLT rate of 30% and an equivalence interval (25%, 33%). A minimum of participants must complete the DLT evaluation period before making an escalation decision. Dose escalation will consist of 4 planned dose levels of sabestomig. Intermediate dose levels may be explored if warranted by emerging safety, PK, pharmacodynamic, biomarker, and efficacy data. Dose escalation and de-escalation recommendations will follow the mTPI-2 algorithm schema below:

- 1 A minimum of evaluable participants are required in each dose level unless unacceptable toxicity is encountered in the first participants prior to enrollment of the third participant, which would require dose de-escalation per the mTPI-2 algorithm. For a dose level that has fewer than participants who are DLT-evaluable, participants will be replaced.
- 2 If a de-escalation decision is made, choice of de-escalation to the previous dose level will be at the discretion of the SRC. In the eventuality that a decision is made to de-escalate back to a dose escalation level that was previously deemed safe, and into which mini expansion cohort participants have since been enrolled at that dose level, these mini-expansion cohort participants may be included in further dose escalation decisions.
- 3 If a stay ("S") decision is made, additional participants will be enrolled up to a maximum of participants for a given dose level.
- 4 Administration of the first dose of sabestomig will be staggered by a minimum of 24 hours between the first and second participants in each dose escalation cohort. Intraparticipant dose escalation will not be allowed during the mTPI-2 part of dose escalation.
- 5 At the discretion of AstraZeneca, dose escalation may be stopped before an MTD is reached.
- 6 The MTD will be determined by isotonic regression analysis applied to DLT rates observed during dose escalation using the mTPI-2 method (Ji et al, 2010).

Participants enrolled into ATD dose escalation cohorts may be considered evaluable for dose escalation decision-making purposes using mTPI-2 algorithm if the dose under investigation is identical to one previously assessed by ATD dose escalation.

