#### Description of the Modified Toxicity Probability Interval-2 Algorithm

The mTPI-2 algorithm employs a simple beta-binomial Bayesian model. The prior distribution for all dose levels is Beta(1,1). The posterior distribution for all dose levels is Beta(1+a, 1+b), where a and b are the number of participants with and without a DLT at the current dose level, respectively. The posterior density of the toxicity probability is divided into multiple intervals with equal length. These intervals are categorized as underdosing, proper dosing, and overdosing in terms of toxicity. The underdosing interval corresponds to a dose escalation, overdosing corresponds to a dose de-escalation, and proper dosing corresponds to staying at the current dose. Given an interval and a probability distribution, the unit probability mass of that interval is defined as the probability of the interval divided by the length of the interval. The design for the dose escalation phase of the study uses a target DLT rate of 30% and an equivalence interval (25%, 33%) for dose escalation/de-escalation decisions as well as MTD determination. A dose level will be considered unsafe, with no additional participants enrolled at that dose level, if it has an estimated 80% or more probability of exceeding the target DLT rate of 30% (ie, Probability  $[DLT > 30\% \text{ data}] \ge 80\%$ ) with at least participants treated and evaluated at that dose level. In Table 15, dose escalation/de-escalation decision rules are computed based on the above information.

Number		Number of Evaluable Participants Treated at Current Dose Level										
of DLTs	1	2	3	4	5	6	7	8	9	10	11	12 °
0	S a	S a	Е	Е	Е	Е	Е	Е	Е	Е	Е	Е
1	S b	S b	S e	S	Е	Е	Е	Е	Е	Е	Е	Е
2		DU d	DU	DU	D	D	S	S	Е	Е	Е	Е
3			DU	DU	DU	DU	DU	D	D	S	S	Е
4				DU	DU	DU	DU	DU	DU	D	D	D
5					DU							

 Table 15
 Modified Toxicity Probability Interval-2 Algorithm

a Changed from "E" to "S" as a minimum of evaluable participants are needed to make a dose escalation decision.

b Changed from "D" to "S" as a minimum of evaluable participants are needed to make a dose escalation decision.

c The "S" cells in original modified toxicity probability interval-2 algorithm are modified to either E or D according to whether the observed DLT rate is < or  $\ge$  the target toxicity of 30%, respectively.

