d If at the first dose level, participants can choose to early terminate the trial or not based on their own discretion.

e Changed from "D" to "S" to ensure the mTPI-2 algorithm performs as conservatively as the standard 3+3 design if a single DLT is observed among the first 3 participants at a new dose level.

Note: Target toxicity (%) is 30% and equivalence interval (25%, 33%). The sample size cap for each dose level will be participants.

Abbreviations: D: de-escalate to the next lower-dose level; DLT: dose-limiting toxicity; DU: current dose is unacceptably toxic; E: escalate to the next higher dose level; S: stay at the current dose level. Sources: Modified from Guo et al, 2017 and Ji et al, 2010.

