After the escalation phase is completed, DLT rates at each dose level are estimated by isotonic regression (Ji et al, 2010). The weighted least squares regression model conditional on monotonic non-decreasing DLT rates with increasing dose and use the empirical (observed) DLT rates at each dose level as responses and sample sizes at each dose level as weights, along with the pool adjacent violators algorithm (PAVA) to estimate the DLT rate at each dose level using available software (eg, Cytel EAST or the function pava() from the R package 'ISO'). Given the DLT estimates for each dose level, the MTD is selected from all tried dose levels that have not been previously declared to be unsafe with a "de-escalate to the previous lower dose and the current dose is never used again due to unacceptable toxicity" (DU) decision according to the mTPI-2 decision table. With this constraint, the MTD is determined as the dose level with the DLT estimate closest to the target toxicity level of "".

For specific dose escalation rules, refer to protocol Section 6.6.1.2.

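### The MTD candidate set drops only the level that itself received a DU decision, so a higher tried level can be named MTD against the plan's own monotone dose-toxicity assumption

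*SAP*

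**What the plan says.** Four places give the same MTD rule: Protocol 6.6.4 and 9.4.3.1, and SAP 3.3.7.1 and 4.5.10.1.

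- **Estimation.** DLT rates are fitted by weighted isotonic regression (PAVA), in the SAP's words "conditional on monotonic non-decreasing DLT rates with increasing dose". Protocol 9.4.3.1 makes the same assumption.
- **Candidates.** SAP 4.5.10.1 states that "the MTD will be selected from all tried dose levels that have not been previously declared to be unsafe", meaning without a DU decision. SAP 3.3.7.1 and both protocol sections agree.
- **Choice.** Among the candidates, the MTD is the level whose isotonic estimate is closest to 30%.
- **Scope of DU.** The mTPI-2 description in Protocol 6.6.1.2 says: "A dose level will be considered unsafe, with no additional participants enrolled at that dose level, if it has an estimated 80% or more probability"; what is meant is a DLT rate above the 30% target. The Table 15 key reads "DU: current dose is unacceptably toxic". Both concern a single level. A D decision only steps down and does not declare the level left behind unsafe.

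No section says what happens to a level already tried above one that receives DU.

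**The concern.** The two halves of the rule do not fit together. A DU decision at level d says that the probability of a DLT rate above 30% there is at least 80%. The monotone assumption says that the rate at d+1 is no lower. Yet d is barred and d+1 is not. When PAVA pools the two levels they share one estimate, so only the candidate set separates them, and it keeps the higher one.

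A higher level can have been tried before d becomes DU in two ways that the protocol foresees: a D decision at d+1 followed by a return to d, or further mini-expansion data at d. Establishing the MTD or OBD is a Part A primary objective. Followed to the letter, the rule could report as maximum tolerated a dose above one that met the plan's own limit for unacceptable toxicity.

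**Working it through.** **Inputs.** Target 30% and equivalence interval 25% to 33% (Protocol 6.6.1.2; the target is redacted in the SAP). Beta(1,1) prior at each level, updated with that level's data only. DU if P(rate > 30%) is at least 0.80. Three to 12 participants per mTPI-2 level (SAP 3.3.7.2).

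**Step 1: reproduce Table 15.** With x DLTs in n participants the posterior is Beta(1+x, 1+n−x). The decision is the category of the interval (length 0.33 − 0.25 = 0.08) with the largest posterior probability divided by length, overridden by DU when the 0.80 limit is met. For the rows with 0 to 4 DLTs, 48 of 54 cells match. The other six (0/1, 0/2, 1/1, 1/2, 1/3, 3/12) are cells that the table's footnotes say were changed by hand.

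**Step 2: a path that uses only Table 15.**

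| Step | Level | DLTs/n | Decision | P(rate > 30%) |
|---|---|---|---|---|
| 1 | d−1 | 0/3 | E | 0.240 |
| 2 | d | 0/3 | E | 0.240 |
| 3 | d+1 | 1/3 | S | 0.652 |
| 4 | d+1 | 2/6 | D | 0.647 |
| 5 | d | 3/6 | DU | 0.874 |

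**Step 3: isotonic estimates.** Raw rates are 0, 0.500 and 0.333. The last two violate monotonicity and pool to (3+2)/(6+6) = 5/12 = 0.417. The estimates are 0, 0.417, 0.417.

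**Step 4: apply the rule.** Level d is barred. Distance from 30% is 0.300 for d−1 and 0.117 for d+1, so d+1 is named. Carrying the DU exclusion upward would name d−1.

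**Step 5: let the escalation run on.** After DU at d the design steps down, so d−1 would normally gain data. At 1/6 its distance is 0.300 − 0.167 = 0.133, and d+1 is still named. At 2/6 its distance is 0.033, and d−1 is named.

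**Step 6: other data.** 0/3, 4/9 (DU, P = 0.850), 2/6 gives 0, 0.40, 0.40 and names the top level. With mini-expansion data, 0/3, 3/7 (DU, P = 0.806), 1/6 gives 0, 0.308, 0.308 and does the same. By contrast, 1/6, 3/6, 2/5 gives 0.167, 0.455, 0.455 and names the lowest level.

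**Step 7: frequency.** Assumptions: four mTPI-2 levels, cohorts of 3, cap 12, 10,000 trials per curve. Percentage of trials with the MTD above a DU level:

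| Assumed DLT rates (%) | Sequential | Mini-expansions filled |
|---|---|---|
| 5, 10, 20, 30 | 0.38 | 0.93 |
| 10, 25, 35, 45 | 1.26 | 1.83 |
| 20, 30, 40, 50 | 0.84 | 1.67 |
| 30, 35, 40, 45 | 0.97 | 1.97 |
| 25, 30, 33, 35 | 1.13 | 2.25 |
| 15, 30, 45, 60 | 1.07 | 1.38 |

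Runs under other assumed curves and stopping details widened the sequential range to about 0.2% to 2%, and gave up to 4.5% when safe levels were filled to 12.

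**The case against.** The strongest reply is that the current rule is not always the worse one. DU uses one level's data, whereas the MTD estimate pools. A DU decision in a small sample can be reversed by pooling: 3/7 (DU, P = 0.806) with 1/12 at the level above pools to 4/19, where P(rate > 30%) is only 0.24. If every true rate is at or below 30%, any dose picked above a DU level is also at or below 30%, and no further from target than a lower choice. In a separate simulation with true rates of 5, 10, 20 and 30%, all 60 such picks in 10,000 trials were of that kind. With 20, 30, 40 and 50%, there were 130 such picks: carrying the exclusion upward chose a dose closer to target in 85 and named no MTD in 45. This stands. A reader might infer that the present rule always errs towards the more toxic dose and that changing it costs nothing; neither holds for every curve. It does not remove the inconsistency, because the plan bars d on its own data and makes no provision for pooling to overturn DU. In the Step 2 example the pooled 5/12 still gives P = 0.835.

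A second reply is that judgement intervenes. Protocol 4.2.1 and 6.6.5 base the RP2D on the OBD and the totality of the data, and 6.6.7 has the SRC review all data before escalation decisions. This limits the consequence but does not alter the MTD rule.

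Third, the method is attributed to a cited paper that may treat higher levels differently. That cannot be checked here; the documents as written do not.

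**Conclusion.** The point stands as an internal inconsistency in the MTD rule. That it can occur rests only on Table 15, the 80% limit and the stated candidate set. How often it occurs rests on assumed toxicity curves, cohort size and stopping details, so the simulated percentages are illustrative; on any of them the event is uncommon. In a purely upward escalation it cannot occur, because nothing above the DU level has been tried.

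A reader might infer that Part B would then be dosed at or up to the wrong level. The documents do not support that: no section makes the MTD a bound on the RP2D. The effect is mainly on the MTD that is reported, and on having to depart from a prespecified rule if the result is judged implausible. The change is worth making because it is small and the present text contradicts its own model.

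**What to change.** Reconcile the candidate set with the monotone assumption in Protocol 6.6.4 and 9.4.3.1 and SAP 3.3.7.1 and 4.5.10.1, with the same sentence in each:

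- State the status of tried levels above a DU level. The form consistent with the isotonic model is that, for MTD estimation, the DU exclusion carries upward, so candidates are the tried levels below the lowest level with a DU decision.
- State what is reported when no candidate remains, for example when the lowest tried level is itself DU.
- Keep reporting the isotonic estimates for all tried levels, including those excluded.

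This concerns how the MTD is estimated, not what dose anyone receives. It needs no extra data or participants, only about one sentence per passage. The statistical cost is small: when a DU decision was a chance finding in a small sample, the reported MTD will be lower than under the current rule, or none will be named. The text should acknowledge this.

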4.5.10.2 Presentations

The MTD evaluation will be based on the DLT evaluable population. The number and percentage of participants with DLT during the dose escalation phase will be presented by treatment groups.

5 INTERIM ANALYSES

participants treated at the RP2D in Part A will be included.

Efficacy interim analyses

Interim analyses will be performed in a continuous manner for Part B

CCI

For each cohort, interim analyses will begin after approximately CCI participants in each respective cohort are included in the interim response-evaluable population. For Cohort B1,

Following this initial interim analysis, subsequent interim analyses may be performed after every additional participants in Cohort B1 and every additional participants in Cohort B2 get included in the interim response-evaluable population, until all participants are enrolled and evaluated. The interim analyses will be conducted to determine futility, where the stopping criteria for futility will be based on the interim response-evaluable set. For any interim futility analyses, an objective response is defined as a CR or PR as per the Modified Lugano criteria and a complete response is defined as a CR as per the Modified Lugano criteria.

Recruitment will not be paused while the participants required for the interim analysis are evaluated. Any decision to stop recruitment in a specific cohort will be at the discretion of AstraZeneca and will be based on emerging efficacy, safety, and tolerability.

Analysis of PFS/OS may be performed at interim analyses using the Interim Response Evaluable population.

Analyses will follow the methodology outlined in this SAP. Outputs presented for the interim analyses will concentrate on ORR, CRR and BoR but may include other outputs, such as PFS/OS. The list of tables, listings and figures required for interim analyses will be flagged in the list of TLFs

Interim Safety analyses

Interim safety analysis will be conducted in Part B after approximately participants have received the first dose for at least to data cut-off, using the interim safety population. Data for both B1 and B2 will be combined. For cohort B1, participants in Part A who are treated at the RP2D will also be included. The study recruitment may be paused, pending investigation by the sponsor in discussion with SRC, if at least one of the following events occur:

7 APPENDICES

Appendix A Response Evaluation Using the Modified Lugano (Cheson et al, JCO 2014) and RECIL (Younes et al, Ann Oncol 2017) Criteria

Measurability of Tumor Lesions

Tumor lesions will be categorized as follows:

Baseline: Baseline assessments are those assessments performed as close as possible to the start of study treatment. Baseline scans will be used to confirm eligibility based on the presence of measurable disease and as reference to assess disease response to study treatment. No anti-lymphoma treatment (including palliative RT) should be implemented between the baseline scans and the first planned dose.

Nodal vs Extranodal: a lesion can be categorized as:

- Nodal (a lymph node or a nodal mass), or
- Extranodal (a lesion located in other organs, including liver and bone marrow;
 Tonsils, Waldever's ring, and spleen are considered nodal tissue).

Measurable Lesions – a measurable lesion is a lesion that can be clearly measured in at least two perpendicular dimensions by CT/MRI (longest diameter [Ldi] and shortest diameter [Sdi]). The Ldi and Sdi will be measured in the transverse plane. A lesion is considered measurable if:

- For nodal lesions: Ldi > 1.5 cm,
- For extranodal lesion (eg hepatic, lung nodules): Ldi > 1 cm,
- The Ldi and the Sdi should be measured on the same slice.

Bulky disease – the presence of a bulky disease is captured by the Ldi on CT scan. For HL, bulky is defined as a single nodal mass, of 10cm or greater than a third of the transthoracic diameter at any level of thoracic vertebrae.

Target Lesions – At baseline, all lesions up to a maximum of 6 measurable nodal or extranodal lesions should be identified as target lesions at baseline and followed throughout the study. It may be the case that, on occasion, the largest lesion does not lend itself to reproducible measurement in which circumstance the next largest lesion which can be measured reproducibly should be selected. Target lesions should be identified from different body regions representative of the participant's overall disease burden and include mediastinal and retroperitoneal disease, if involved. A bulky lesion can also be selected as target lesion. Target lesions must meet the measurability criteria and show FDG-avid uptake. Lesions visible on PET but not measurable on CT/MRI should be assigned as non-target lesions. When selecting the target lesions, consider the following;

- Target lesions should be identified from different body regions representative of the participant's overall disease burden and include mediastinal and retroperitoneal disease, if involved.
- A bulky lesion can also be selected as target lesion.

- Target lesions should be selected from those of the largest size that can be measured reproducibly.
- In certain anatomical sites (inguinal, axillary, and portocaval), normal lymph nodes may exist in a very narrow, elongated form. Clinical judgment should be used when selecting these lesions are target lesions.
- Because of the variable anatomical coverage of scans at different timepoints, it is preferrable not to select as target lesions nodal lesions located in the higher cervical and/or lower inguinal districts.

For the selected target lesions, the sum of the product of the perpendicular diameters (SPD) will be calculated with the percentage change from baseline for assessment of response and nadir for assessment of progression.

Non-target Lesions – All other lesions (including nodal, extranodal, and assessable disease) not selected as target lesions, as well as truly non-measurable sites of disease should be followed as non-measurable disease (eg. Cutaneous, gastrointestinal, bone, spleen, liver, kidney, pleural or pericardial effusions, ascites) and should be factored into the overall response assessment. Non-target lesions will be documented at baseline and throughout the study qualitatively (for example: present, absent/normalized /clear progression). Measurement of these lesions is not required to be documented in the eCRF.

Organ Involvement

Spleen involvement: Spleen will be considered to be normal if size of its vertical length (cranial-caudal measurement) is ≤ 13 cm. Spleen vertical length will be assessed at screening and all subsequent response-evaluations. Splenic nodules should be considered as extra-nodal lesions and treated as target, non-target or new lesions are appropriate.

Liver involvement: Given variability in body habitus and the impact of numerous medical conditions, liver size by physical examination or CT scan is not a reliable measure of hepatic involvement by lymphoma. For these reasons, liver size will not be collected in eCRFs. The presence of a diffuse or focal uptake with or without focal or disseminated nodules support liver involvement. Intrahepatic lesions should be considered as target, non-target, or new lesion as applicable.

Bone Marrow involvement: Bone marrow involvement by lymphoma documented by biopsy and/or aspirate or by PET will be reported on the eCRF as positive, negative or unknown.

Other, skin and soft tissue lesions: Skin lesions histologically proven for lymphoma should be preferably selected as Non-target lesions due to variability in measurement on skin photography. If skin is the only site of measurable disease, colour photographs including a ruler should be submitted to BICR (as applicable) and stored in medical records. Measurements should be reported in eCRFs at each disease response assessment if these lesions are selected as target lesions

New Lesions – Lesions which were not present at the baseline, but are visible at a subsequent timepoint:

Nodal lesion of > 1.5 cm in any axis,

Extranodal lesion of > 1 cm in any axis.

In case of appearance of a new extranodal lesion ≤ 1 cm, a biopsy confirmation of lymphoma is always preferable to rule out a benign origin, unless not feasible (lesions too small) or if the procedure is medically contraindicated. The appearance of a new lesion, even if all other lesions are decreasing should be considered progression.

Staging and Classification

Stage: Extent of disease should be described at baseline using the Revised Ann Arbor classification (Table 2).

Symptoms: according to the absence (A) or presence (B) of disease related symptoms. Only participants with HL need to be assigned the designations A or B because symptoms only direct treatment in that disease.

Stage	Stage Involvement Extranodal (E) Stage	
Limited		
I	One node or a group of adjacent nodes	Single extranodal lesions without nodal involvement
II	Two or more nodal groups on the same side of the diaphragm	Stage I or II by nodal extent with limited contiguous extranodal involvement
ll bulky*	II as above with "bulky" disease	Not applicable
Advanced		
III	Nodes on both sides of the diaphragm; nodes above the diaphragm with spleen involvement	Not applicable
IV	Additional noncontiguous extralymphatic involvement	Not applicable

NOTE. Extent of disease is determined by positron emission tomographycomputed tomography for avid lymphomas and computed tomography for nonavid histologies. Tonsils, Waldeyer's ring, and spleen are considered nodal tissue.

"Whether stage II bulky disease is treated as limited or advanced disease may be determined by histology and a number of prognostic factors.

Modified Lugano Response-evaluation Criteria (Cheson et al, 2014)

Response and Site	PET-CT-Based Response	CT-Based Response
Complete	Complete metabolic response	Complete radiologic response (all of the following)
Lymph nodes and extralymphatic sites	Score 1, 2, or 3" with or without a residual mass on SPS† It is recognized that in Waldeyer's ring or extranodal sites with high physiologic uptake or with activation within spleen or marrow (eg. with chemotherapy or myeloid colony-stimulating factors), uptake may be greater than normal mediastinum and/or liver. In this circumstance, complete metabolic response may be inferred if uptake at sites of initial involvement is no greater than surrounding normal tissue even if the tissue has high physiologic	Terget nodes/nodal masses must regress to ≤ 1.5 cm in LI No extralymphatic sites of disease
	uptake	
Normessured lesion	Not applicable	Absent
Organ enlargement	Not applicable	Regress to normal
New lesions	None	None
Bone marrow	No evidence of FDG-avid disease in marrow	Normal by morphology; if indeterminate, IHC negative
Partial Lymph nodes and extralymphatic sites	Partial metabolic response Score 4 or 6+ with reduced uptake compared with baseline and residual massles) of any size	Partial remission (all of the following) ≥ 50% decrease in SPD of up to 6 target measurable node and extranodal sites
	At interim, these findings suggest responding disease	When a lesion is too small to measure on CT, assign 5 mm × 5 mm as the default value
	At end of treatment, these findings indicate residual disease	When no longer visible, 0 × 0 mm For a node > 5 mm × 5 mm, but smaller than normal, use actual measurement for calculation
Normessured lesions	Not applicable	Absent/normal, regressed, but no increase
Organ enlargement	Not applicable	Spleen must have regressed by > 50% in length beyond normal
New lesions	None	None
Bone marrow	Residual uptake higher than uptake in normal marrow but reduced compared with baseline (diffuse uptake compatible with reactive changes from chemotherapy allowed). If there are persistent focal changes in the marrow in the context of a nodal response, consideration should be given to further evaluation with MRI or biopsy or an interval scan	Not applicable
No response or stable disease	No metabolic response	Stable disease
Target nodes/nodal masses, extranodal lesions	Score 4 or 5 with no significant change in FDG uptake from baseline at interim or end of treatment	< 50% decrease from baseline in SPD of up to 6 dominant measurable nodes and extranodal sites; no criteria for progressivo disease are mot
Nonmeasured lesions	Not applicable	No increase consistent with progression
Organ enlargement	Not applicable	No increase consistent with progression
New lesions	None	None
Bone marrow	No change from baseline	Not applicable
Progressive disease Individual target nodes/nodal masses	Progressive metabolic disease Score 4 or 5 with an increase in intensity of uptake from baseline and/or	Progressive disease requires at least 1 of the following PPD progression:
Extranodal lesions	New FDG-avid foci consistent with lymphoma at interim or end-of-treatment ecoesament	An individual node/lasion must be abnormal with: LDi > 1.5 cm and Increase by ≥ 50% from PPD nadir and An increase in LDi or SDi from nadir 0.5 cm for lesions ≤ 2 cm 1.0 cm for lesions > 2 cm In the setting of splenomegaly, the splenic length must increase by > 50% of the extent of its prior increase beyond baseline [eg., a 15-cm splenomegaly, must increase to > 16 cm). If no prior splenomegaly, must increase by at least 2 cm from baseline New or recurrent splenomegaly
Normeasured lesions	None	New or clear progression of preexisting nonmeasured lesions
	(continued on following page)	

	Table 3. Revised Criteria for Response Assessment (continued)			
Response and Site	PET-CT-Based Response	CT-Based Response		
New lesions	New FDC-avid foci consistent with lymphoma rather than another etiology (eg, infection, inflammation). If uncertain regarding etiology of new lesions, biopsy or interval scan may be considered	Regrowth of previously resolved lesions A new node > 1.5 cm in any axis A new extranodal site > 1.0 cm in any axis; if < 1.0 cm in any axis, its presence must be unequivocal and must be attributable to lymphoma Assessable disease of any size unequivocally attributable to lymphoma		
Bone marrow	New or recurrent FDG-avid foci	New or recurrent involvement		

Abbreviations: SPS, 5-point scale; CT, computed tomography; FDG, fluorodeoxyglucose; IHC, immunohistochemistry; LDi, longest transverse diameter of a lesion; MRI, magnetic resonance imaging; PET, positron emission tomography; PPD, cross product of the LDi and perpendicular diameter; SDi, shortest axis perpendicular to the LDi; SPD, sum of the product of the perpendicular diameters for multiple lesions.

"A score of 3 in many patients indicates a good prognosis with standard freatment, especially if at the time of an interim scan. However, in trials involving PET where de-escalation is investigated, it may be preferable to consider a score of 3 as inadequate response ito avoid undertreatment! Measured dominant lesions: Up to six of the largest dominant nodes, nodal masses, and extranodal lesions selected to be clearly measurable in two diameters. Nodes should preferably be from disparate regions of the body and should include, where applicable, mediastinal and retroportional areas. Non-nodal lesions include those in solid organs (eg. liver, spleen, kidneys, lungs), GI involvement, cutaneous lesions, or those noted on palpation. Nonmeasured lesions: Any disease not selected as measured, dominant disease and truly assessable disease should be considered not measured. These sites include any nodes, nodal masses, and extranodal sites not selected as dominant or measurable or that do not meet the requirements for measurability but are still considered abnormal, as well as truly assessable disease, which is any site of suspected disease that would be difficult to follow quantitatively with measurement, including pleural effusions, ascites, bone lesions, leptomeningeal disease, abdominal masses, and other lesions that cannot be confirmed and followed by imaging. In Waldeyer's ring or in extranodal sites (eg. CI tract, liver, bone marrow), FDG uptake may be greater than in the mediastinum with complete metabolic growth factors).

Deauville 5-point scale: The use of PET/CT is standard for FDG-avid lymphomas and whenever aggressive transformation is suspected. Variation in FDG uptake in a nodal or extranodal sites indicative for lymphoma will be visually assessed using the Deauville 5-point scale. The scale ranges from 1 to 5, where 1 is best and 5 is the worst. Each FDG-avid (or previously FDG-avid) lesion is rated independently.

Deauville 5-point scale

Score	Description		
Score 1	No uptake above background		
Score 2	Uptake ≤ mediastinum		
Score 3	Uptake $>$ mediastinum, but \leq liver		
Score 4	Uptake moderately > liver ^a		
Score 5	Uptake markedly higher than liver and/or new lesion ^a		
X (New)	Areas of uptake unlikely to be related to lymphoma ^b		

^a Barrington et al (2014) suggest the following: "The terms moderately and markedly were not defined initially, because there were insufficient data to define scores quantitatively. Meanwhile, it is suggested according to published data that score 4 be applied to uptake greater than the maximum SUV in a large region of normal liver and score 5 to uptake 2 × to 3 × greater than the maximum SUV in the liver."

^b Barrington SF, Mikhaeel NG, Kostakoglu L, et al: Role of imaging in the staging and response assessment of lymphoma: Consensus of the International Conference on Malignant Lymphomas Imaging Working Group. J Clin Oncol 32:3048-3058, 2014

SUV: standardized uptake value.

It is recognized that in Waldeyer's ring or extranodal sites with high physiologic uptake or with activation within spleen or bone marrow (eg, following chemotherapy or G-CSF treatment), the uptake may be greater than normal mediastinum and/or liver. In this circumstance, complete CR may be inferred if uptake at sites of initial involvement is no greater than surrounding normal tissue even if the tissue has high physiologic uptake. In presence of new areas of FDG uptake that are unlikely to be related to lymphoma but are thought to be of inflammatory or infectious origin by the Investigator, the reporter should assign 'X' in addition to the Deauville score. For example, if there is a complete resolution of all uptake with no abnormal nodes but new lesions likely to be related to another etiology occur, the total score should be of DS 1X rather than DS 5. Additionally, these lesions should be tracked and should not be used to determine the PET response at subsequent assessments.

Evaluation of Overall Response

The table below provides overall responses for all possible combinations of tumor responses in target and non-target lesions with or without the appearance of new lesions.

Evaluation of Overall Response Using the Modified Lugano Criteria

Target Lesions	Non-target Lesions	New Lesions	Overall Response
CR	CR	No	CR
No target lesion a	CR	No	CR
CR	Not evaluable ^b	No	PR
CR	Non-CR/ non-PD	No	PR
PR	Non-PD and not evaluable ^b	No	PR
Stable disease	Non-PD and not evaluable ^b	No	Stable disease
Not all evaluated	Non-PD	No	Not evaluable
No target lesion a	Not all evaluated	No	Not evaluable
No target lesion a	Non-CR/ non-PD	No	Non-CR/ non-PD
PD	Any	Yes/No	PD
Any	Unequivocal PD	Yes/No	PD
Any	Any	Yes	PD
No target lesion a	Unequivocal PD	Yes/No	PD
No target lesion a	Any	Yes	PD

– ed. 3.0

a Defined as no target lesion at baseline.

b Not evaluable is defined as either when no or only a subset of lesion measurements are made at an assessment.

Abbreviation: CR: complete response; PD: progressive disease; PR: partial response.

Modified Lugano: Response-evaluated Criteria

Integrated Radiological Overall Response

PET-based	CT/MRI-based	Radiological
Overall Response	Overall Response	Overall Response
CMR	Any b	CR
PMR	Any b	PR
NMR	Any b	SD
UNK.	CR/PR/SD + prior PET response of CMR (as long as the CT	CR
	response remains stable/improves as compared to the previous timepoint when PET was available)	
UNK .	CR/PR + prior PET PMR or no PET (as long as the CT response	PR
	remains stable/improves as compared to the previous timepoint when PET was available)	
UNK .	CR/PR + prior PET NMR	SD
UNK *	Any response except for PD (but has worsened from the previous	UNK
	timepoint when PET was available)	
UNK *	UNK	UNK
UNK *	PD	PD
PMD	Any	PD

PET not done/not available

Depending on the histology of the lymphoma. For lymphomas with variable avidity, CT PD could lead to an overall assessment of PD

CMR: complete metabolic response; CR: complete response; NMR: no metabolic response; PD: progressive disease; PMD: progressive metabolic disease; PR: partial response; SD: stable disease; UNK: unknown.

Overall Response Assessment

Radiological	Bone Marrow	Clinical findings (Physical	Overall Response
Overall Response	Aspirate/Biopsy	Examination/ Lesion Biopsy)	Assessment
CR	Negative (+ 28 days from	No evidence of PD	CR
	radiological assessment) or negative at baseline		
CR	Positive at baseline and positive (no	No evidence of PD	PR
	new involvement) + 28 days from radiological assessment; or positive at the previous timepoint and not repeated		
PR/SD	Any but new or recurrent	No evidence of PD	PR/SD

	-	•
α	4	•
Cu.		u

	involvement		
PD	Any	Any	PD
Any	New or recurrent BM involvement	Any	PD
Any	Any	New or recurrent lymphoma	PD
		manifestation	

BM: bone marrow; CR: complete response; PD: progressive disease; PR: partial response; SD: stable disease; UNK: unknown.

Additional response assessment guidelines:

Nodes or Extranodal lesions that split when disease is responding: If a confluent nodal
